## 6.2 Analysis methods

Analyses will follow CONSORT guidelines (Campbell, Piaggio, Elbourne, & Altman, 2012; Piaggio et al., 2012; Schulz, Altman, & Moher, 2010; Zwarenstein et al., 2008). Outcomes will be described by arm using summary statistics. For the non-inferiority comparison between ePOCT+ and the control arm for clinical failure, a CI approach will be used using a random effects logistic regression model using the cluster (health facility) and patient as random effects. A figure illustrating the 95% CIs of the ITT and PP relative risk of clinical failure will be presented with the pre-specified non-inferiority margin of 1.3. Non-inferiority will be achieved if the upper-bound of the RR does not surpass 1.3. If ePOCT+ is found to be

non-inferior to the control in terms of clinical failure using the PP population, then we will assess for superiority using the ITT population. Superiority will be achieved if the relative risk CI of the ITT set does not surpass 1. If clinical failure non-inferiority is established, we will test for significant differences in the co-primary outcome of antibiotic prescription rate. Since the documentation of the final treatment in both arms is part of the per protocol definition, only the PP population can be used. For this outcome, the percentage of patients receiving antibiotics at the initial consultation will also be assessed using a random effects logistic regression model with the cluster (health facility) and patient included as random effects. Binary secondary outcomes and additional analyses will be evaluated in the same way. All estimates will be reported with two-sided 95% confidence intervals (CI), except for the non-inferiority analysis which will be reported with one-sided 95% CI. The study will be deemed a success if clinical failure in the ePOCT+ arm is non-inferior to the control arm, and antibiotic prescription at the initial consultation is 25% less in the ePOCT+ arm compared to the control arm.

Effect modification of the co-primary outcomes of antibiotic prescription and clinical failure will be performed in groups of patients where the highest reduction in antibiotic prescription is expected, and areas of extension of the content of the algorithm compared to the version tested in the previous ePOCT study. Effect modification by sex, age group (young infants ages 1 to 59 days, children aged 2 months to 5 years, and children aged 5 to 14 years), respiratory symptoms, fever without clinical source, gastrointestinal complaints (vomiting and diarrhea), skin problems, ear, nose and throat problems, will be assessed by incorporating an interaction between arm and the respective variable, acknowledging that power will be low. All models will be adjusted for clustering and the stratification factors (Kahan & Morris, 2012). Furthermore in order to adjust for potential imbalances in baseline characteristics between study groups, relevant baseline characteristics will be included as fixed effect variables in the final model. Baseline characteristic imbalance will be determined by consensus among the study analysis team.

The number of children lost to follow up may be quite high due to the difficult nature of phone follow-up at day 7, as found in previous studies with day 7 phone call lost to follow up rates of 13-25% (Christie et al., 2018; Hannigan, Chisale, Drew, Watson, & Gallagher, 2019; Nguhuni et al., 2017). Comparatively, the proportion not cured at day 7 is expected to be quite low (3%). The use of a complete case analysis was therefore selected for the non-inferiority co-primary outcome of day 7 clinical cure, as it would be the most conservative analysis. If we were to use the “enrolled set” and considered all day 7 lost to follow up as not being cured, this would dilute the difference between arms, and thus may demonstrate non-inferiority when there is truly a difference between arms (type 1 error). Not considering lost to follow up cases as failures is also the approach used for similar studies with high number of LTF and low proportion of outcomes (Källander et al., 2018). We may adjust the final model for further baseline variables (not already included as fixed effect variables) which are associated with missing outcome data (analogous to performing multiple imputation in the case of a single endpoint). As with the other fixed effect variables, baseline characteristic imbalances among patients lost to follow up will be determined by consensus among the study analysis team.

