Analyses will follow CONSORT guidelines (Schulz et al. 2010, Piaggio et al. 2012) and intention-totreat (ITT) principles, that is including all participants as randomized. A flowchart will describe the inclusion and follow-up of participants by study arm. Baseline characteristics will be described by study arm with summary statistics such as median and interquartile range or number and percentage; no formal testing between arms will be performed (Pocock et al. 2002). Outcomes will be described by arm using summary statistics. For the non-inferiority comparison between ePOCT+ and the control arm for clinical cure, a CI approach will be used. A figure illustrating the CIs and the non-inferiority margin will be presented. Primary analyses for the non-inferiority comparison will be performed on both the per protocol and ITT sets (Committee for Proprietary Medicinal P 2001). If ePOCT+ is found to be non-inferior to the control in terms of clinical cure rate, then we will assess for superiority using the ITT set. If non-inferiority is established, we will test for significant differences in the co-primary outcome of antibiotic prescription rate. For this outcome, the percentage of patients receiving antibiotics at day 0 will be assessed using multi-level logistic regression model regression with the cluster included as a random effect. Binary secondary outcomes will be evaluated in the same way. All estimates will be reported with 95% confidence intervals (CI).

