## 3.3 Sample size

The primary analysis will evaluate whether the use of ePOCT+ for case management of sick children in PHC facilities 1) results in similar clinical cure at day 7 (non-inferiority analysis), as compared to routine care and 2) decreased antibiotic prescriptions (superiority analysis) at the initial consultation. The sample size was calculated for testing the non-inferiority of the clinical cure outcome, which will require a much larger sample size due to the rareness of clinical failure. In addition, the testing of differences in antibiotic prescription is conditional on satisfying non-inferiority in the clinical outcome. Assuming a failure rate (not being cured at day 7) of 3% in the control arm (corresponding to a 97% clinical cure rate), based on previous studies, the acceptable non-inferiority margin will be a risk ratio of 1.3. This corresponds to the upper bound of the difference in failure rate not exceeding 0.9% if the control group failure rate is 3%. We utilized a fixed risk ratio rather than an absolute risk difference to protect against potential unexpected event rates (Head et al. 2012).

We assumed a cluster size of 900 patients (average of 150 patients per month x 6 months) and an intraclass correlation coefficient of 0.002 in the clinical outcome based on similar studies. To have 80% power to detect a risk ratio 1.3, for a one-sided hypothesis test at alpha of 0.025, we would require 19 clusters and 17,100 patients per arm (total patients n=37,620 assuming 10% loss to follow-up), rounded to a total of 40 HFs and 40,000 patients. However, due to uncertainty regarding the assumptions of the sample size calculation and to capture a wider more representative range of conditions, we will continue recruitment for Phase 1 for a minimum of 6 months.

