### 6.3 Exploratory analyses

Unless specifically described, the following analyses will be analyzed similarly to the binary secondary outcomes, using a random effects logistic regression model with the cluster (health facility) and patient included as a random effect.

- % of children hospitalized among those referred for hospitalization during an initial consultation

Timing and method of measurement: Hospitalization determined by day 7 (6-14) phone call or home visit. Referral for hospitalization as determined by eCRF during the initial consultation.

- % of children referred for malnutrition management during the initial consultation

Timing and method of measurement: Referred for malnutrition as documented in eCRF during the initial consultation.

- % of children referred for or performed at the health facility tuberculosis screening during the initial consultation

Timing and method of measurement: As documented in the eCRF during the initial consultation.

- % of children tested for HIV during the initial consultation:

Timing and method of measurement: As documented in the eCRF during the initial consultation.

- % of children tested for any laboratory test during the initial consultation:

Timing and method of measurement: As documented in the eCRF during the initial consultation

- % of clinicians accepting the ePOCT+ testing, treatment, diagnosis, and management recommendations during the initial consultation

Timing and method of measurement: As documented in the eCRF of the intervention arm (ePOCT+) during the initial consultation

- % of children/caretakers seeking additional medications after the initial consultation

Timing and method of measurement: Asking caretakers if they procured additional medications for their child after the initial consultation by phone call or home visit at day 7 (6-14)

- Change in % of children with antibiotic prescribed over time

Timing and method of measurement: Antibiotic prescription as documented in the eCRF (control arm) / ePOCT+ tool (intervention) during the initial visit (day 0).

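### The SAP's binary models add a patient random intercept identified only by re-enrolled children; with fitting method and RR derivation left open, the limit judged against 1.3 can be wrong in either direction

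*SAP*

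**What the plan says.** SAP 6.2 fits the non-inferiority comparison by "a CI approach will be used using a random effects logistic regression model using the cluster (health facility) and patient as random effects". For antibiotic prescription it repeats "using a random effects logistic regression model with the cluster (health facility) and patient included as random effects", and it extends the method to the binary secondary outcomes. SAP 6.3 makes it the default for exploratory outcomes, "using a random effects logistic regression model with the cluster (health facility) and patient included as a random effect".

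Protocol 10.3 specifies, for antibiotic prescription and the binary secondary outcomes, a "multi-level logistic regression model regression with the cluster included as a random effect". For non-inferiority of cure it promises only a confidence-interval approach, and it leaves further detail to the SAP. The SAP gives no reason for adding the patient effect.

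The decision rule in SAP 6.2 is on the risk-ratio scale: "Non-inferiority will be achieved if the upper-bound of the RR does not surpass 1.3". SAP 3.3 sets the same margin: "the acceptable non-inferiority margin will be a risk ratio of 1.3". No text says how a risk ratio and its interval are derived from the logistic model, or which estimation method is used.

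**The concern.** A random intercept for patient needs several records from the same patient. Under SAP 6.1.1 each enrolment gives one prescription decision at day 0 and one clinical status at day 7. A child enrolled once therefore contributes one binary value per outcome and carries no information on the patient variance. Only children enrolled again do. The documents do not say whether a child may be re-enrolled in Phase 1, or how often that is expected.

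A weakly identified variance is harmless if the reported quantity does not depend on it. It does harm if the numerical approximation fills the gap, or if a child-specific odds ratio is read as the risk ratio. The SAP rules out neither. The result at stake is the non-inferiority verdict on clinical failure, which also decides whether antibiotic prescription is tested at all.

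**Working it through.** **1. The plan's own figure.** Inputs from SAP 3.3: "Assuming a failure rate (not being cured at day 7) of 3% in the control arm", margin 0.9 points, one-sided alpha 0.025, power 80%, 900 per cluster, ICC 0.002.
- Per arm without clustering: (1.96 + 0.8416)² × 2 × 0.03 × 0.97 / 0.009² = 5,640.
- Design effect: 1 + 899 × 0.002 = 2.798, giving 15,781 patients, or 17.5 clusters.
- The usual one extra cluster gives about 18.5, rounded up to 19. Then 19 × 900 = 17,100 per arm, and 34,200 × 1.1 = 37,620.

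The plan's figure is reproduced. It contains a facility ICC and no within-child correlation.

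**2. Is the patient variance identified?** Simulated trials: 40 facilities × 900 records, 3% failure in both arms, facility SD 0.262 on the logit scale (0.262² × 0.03 × 0.97 = 0.002). Assumed: patient SD 1, and 0, 2, 5 or 20% of children with two records. Fitting was by accurate quadrature, 60 trials per scenario.
- No repeats: the log-likelihood changes by 0.11 on average as the patient SD goes from 0.1 to 5. The fit stays near its starting value (median 1.00 from start 1, 2.98 from start 3).
- With repeats, 5th to 95th percentile of the fitted SD: 0.02 to 1.73 (2%), 0.02 to 1.42 (5%), 0.63 to 1.31 (20%).

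**3. Does it move the limit when fitted accurately?** Mean upper limit (z = 1.96) of the standardised risk ratio:

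| Children with two records | Facility only | Facility + patient |
|---|---|---|
| 0% | 1.193 | 1.193 |
| 2% | 1.223 | 1.223 |
| 5% | 1.231 | 1.231 |
| 20% | 1.208 | 1.208 |

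The largest difference in any trial was 0.009, and the verdict against 1.3 never changed.

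The conditional odds ratio behaves differently. In one trial without repeats its upper limit was 1.227, 1.237, 1.365 and 1.585 at patient SD 0.1, 1, 3 and 5, with practically the same likelihood. Read against 1.3, it changed the verdict between the two starting values in 38% of trials without repeats, and in 0 to 2% with 2 to 20% repeats. For scale, a risk ratio of 1.3 at 3% failure is an odds ratio of (0.039/0.961)/(0.03/0.97) = 1.31. It becomes a conditional odds ratio of 1.34 at patient SD 1.3 and 1.53 at SD 3.

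**4. What if the fit is approximate?** Expected counts, 17,100 records per arm, 3% failure, no true within-child correlation, no facility effect. At each fixed patient SD σ the intercept β was re-estimated by Laplace. With I the information on the intercept in one arm, SE(log OR) = √(2/I). Implied marginal failure is m = E[expit(β + σu)], with u standard normal. SE(log RR) = SE(log OR) × (dm/dβ)/m. With 5% of children having two records:

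| Patient SD | Log-likelihood | SE log OR | Implied failure | SE standardised log RR |
|---|---|---|---|---|
| 0.1 | −4608 | 0.063 | 3% | 0.062 |
| 10 | −2338 | 0.165 | 18% | 0.024 |
| 15 | −2110 | 0.212 | 24% | 0.018 |

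The likelihood was still rising at SD 15, the largest value tried, for 0, 2, 5 and 20% repeats. Across SD 10 to 15 and these shares, the SE of the log odds ratio was 0.162 to 0.225, about 2.5- to 3.5-fold (0.162/0.063 = 2.6; 0.225/0.063 = 3.6). Seven-point adaptive quadrature also favoured SD 10 to 15 over small values, though with a shallow dip near SD 3, so a fit started low might stop there.

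**The case against.** The strongest reply is that the patient term is deliberate and harmless. Eligibility (Protocol 5.1, SAP 5.2.2) does not exclude earlier enrolment. An initial consultation can be read per acute problem. The study ID links former consultations (Protocol 8.1.8), and Protocol 10.2 expects repeat attendance in Phase 2. The margin is a risk ratio, and on that scale step 3 shows no effect. Protocol 10.3 leaves detail to the SAP, so the added term is not a contradiction.

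Most of this stands. A reader might infer that nearly every child has one record, but the documents do not say so; it is suggested only by the planning text, which counts 17,100 records as 17,100 children. A reader might also infer that the non-inferiority interval depends on fitting noise whatever is done; step 3 refutes that for an accurate fit with a standardised risk ratio. What does not stand is that repeats cure the problem: under Laplace they do not, even at 20%. Nor does the SAP commit to the accurate fit or the standardised risk ratio on which the reply relies.

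**Conclusion.** The point holds in a limited form. The patient intercept adds nothing useful to the decision when fitted accurately, and it exposes the decision to numerical error when it is not. The error can run either way: an inflated standard error on the odds-ratio scale, or a falsely narrow interval on the standardised risk-ratio scale. For a safety comparison the second is worse.

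Two power figures should not be over-read. With 20 × 900 per arm, the binomial SE is √(2 × 0.97/(18,000 × 0.03)) = 0.060. Times √2.798 this is 0.100, and power is Φ(0.262/0.100 − 1.96) = 74%.
- A reader might blame the patient term for a fall to 72%. That is the ordinary gap between log odds ratio and log risk ratio at 3% failure, 1/(1 − 0.03) = 1.03, which a facility-only logistic model shares.
- A figure of about 27% arises if the binomial part triples: √(0.180² + 0.100² − 0.060²) = 0.197. It applies only to a Laplace fit read on the odds-ratio scale.

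The result rests on assumed repeat shares, an assumed patient SD of 1 in steps 2 and 3, only 60 trials per scenario, and a step 4 without a facility effect. Step 4 shows distorted standard errors; it does not estimate how often the verdict would be wrong.

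**What to change.** In SAP 6.2 and 6.3, delete *and patient*, so that facility is the only random effect. This matches Protocol 10.3 for antibiotic prescription and the binary secondary outcomes. At 900 records and 3% failure a facility contributes about 27 failures, so its intercept does not share the one-record problem.

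Add to SAP 6.2 that the risk ratio and its interval are obtained by marginal standardisation from the fitted model, and name the fitting method.

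State whether a child may be enrolled more than once in Phase 1, and report how many were. Add a sensitivity analysis comparing first enrolments only with all episodes, using facility-level robust standard errors and a small-sample correction for 40 clusters.

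The cost is SAP wording and one sensitivity analysis. The downside is that within-child correlation is then handled only through the facility level and that sensitivity analysis. A child who attends two participating facilities (foreseen in Protocol 8.1.3) is covered only by the first-enrolment analysis.

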## 3.2 Randomization

The 40 health facilities to be included in the study will be randomly selected from all eligible health facilities in the participating councils (Mlimba district council, Ulanga district council, Ifakara town council, Mbeya district council, and Mbeya city council). Eligible health facilities include public health centers and dispensaries with at least 20 consultations with children between 2 months and 5 years of age per week. Cluster inclusion and exclusion criteria will first be applied to the full list of health facilities in the participating councils prior to selection and randomization. The random selection will follow a 3:2 ratio of health facilities between Morogoro and Mbeya regions, respectively, and include exactly 4 health centers per region.

Health facilities (or clusters) will be randomized (1:1), to using ePOCT+ (intervention) or routine care (control group). Randomization will be stratified by council, type of health facility (health center versus dispensary), and attendance rate. An independent statistician will perform both the sampling and randomization.

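### SAP 6.2 specifies no small-sample method for 40 facilities; if fitted by maximum likelihood with a Wald z bound, the one-sided non-inferiority error is about 4.5% rather than 2.5%

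*SAP*

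**What the plan says.** SAP 3.2 randomises facilities 1:1 and states: "Randomization will be stratified by council, type of health facility (health center versus dispensary), and attendance rate". It names five councils but gives no categories for attendance rate. SAP 3.3 arrives at a trial "rounded to a total of 40 HFs and 40,000 patients", with the calculation made "for a one-sided hypothesis test at alpha of 0.025".

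For the non-inferiority comparison of clinical failure, SAP 6.2 plans "a CI approach will be used using a random effects logistic regression model using the cluster (health facility) and patient as random effects". The same kind of model is used for antibiotic prescription and for the binary secondary outcomes. SAP 6.2 then adds: "All models will be adjusted for clustering and the stratification factors". Further baseline characteristics may enter as fixed effects, chosen by consensus of the analysis team.

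SAP 6.2 gives the interval level as two-sided 95% throughout, "except for the non-inferiority analysis which will be reported with one-sided 95% CI". It also promises "A figure illustrating the 95% CIs of the ITT and PP relative risk of clinical failure" without saying whether those are one- or two-sided.

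Protocol 10.3 defers further detail to the SAP. Neither document states the estimator, the reference distribution, the degrees of freedom or any small-sample correction.

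**The concern.** The arm effect is a comparison between facilities. With an ICC of 0.002 and 900 children per facility, 899 × 0.002 = 1.798 of the design effect of 2.798, or 64% of the variance of the arm comparison, comes from differences between facilities. Tens of thousands of children do not change the fact that there are 40 independent units.

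Maximum likelihood does not correct the between-facility variance for the facility-level coefficients it estimates, so the standard error is too small. A z bound then ignores that few degrees of freedom remain. The required stratification terms make both effects worse.

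Non-inferiority on clinical failure is the safety claim, and it gates the test of antibiotic prescription. If its error rate depends on an unstated software choice, that choice could be made after the data are seen.

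**Working it through.** **Inputs.** 40 facilities, 20 per arm; ICC 0.002; cluster size 900; control failure 3%; margin risk ratio 1.3 (0.9 points at 3%); one-sided alpha 0.025; 80% power (all SAP 3.3). Five councils, two facility types, attendance rate (SAP 3.2). One attendance term is an assumption.

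**Step 1: the plan's own figure.** Per arm without clustering: (1.96 + 0.842)² × 2 × 0.03 × 0.97 / 0.009² = 5,640. Times 2.798 this is 15,781, or 17.53 clusters of 900. Adding one cluster per arm, or using t quantiles on 36 df, gives 18.53, rounded up to 19 clusters and 17,100 children. Then 34,200 × 1.10 = 37,620. The stated figures are reproduced.

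**Step 2: facility-level parameters.** Intercept 1, arm 1, council 4, type 1, attendance 1: 8 in all, leaving 40 − 8 = 32 df.

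**Step 3: closed form.** Maximum likelihood in effect divides the between-facility sum of squares by 40 instead of 32. The error of a nominal 2.5% Wald z bound is then

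P(t₃₂ > 1.96 × √(32/40)) = P(t₃₂ > 1.753) = 4.46%.

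- With 7 facility-level coefficients: 4.2%. With 10: 5.0%.
- With an unbiased variance and only z in place of t: P(t₃₂ > 1.96) = 2.9%. Most of the excess therefore comes from the variance, not from the quantile.
- For a one-sided 95% bound: P(t₃₂ > 1.645 × √(32/40)) = 7.5% against 5%.

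**Step 4: simulation.** Random-intercept logistic model for facility, full maximum likelihood by quadrature. Simulation A: 10,000 trials, 855 evaluable per facility (34,200/40), true odds ratio 1.3, Monte Carlo SE about 0.2 points. Simulation B: 20,000 trials, 900 per facility, true marginal risk ratio 1.3, Monte Carlo SE 0.15 points.

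| Analysis at nominal 2.5% | A | B |
|---|---|---|
| ML, z, no stratification terms | 3.2% | 3.1% |
| ML, z, stratification terms | 4.5% | 4.5% |
| ML, t on 32 df, variance unchanged | 4.1% | 3.9% |
| ML variance × 40/32, t on 32 df | – | 2.4% |
| Facility-level log-odds regression, t on 32 df | 2.6% | – |

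In B the adjusted model's mean standard error was 0.0918 against an empirical SD of 0.1033. The ratio, 0.889, is close to √(32/40) = 0.894, which supports the closed form.

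**Step 5: sensitivity (B settings, ML with z).** The error stayed between 4.1% and 4.9% for ICC 0.0005 to 0.005, equal or unequal clusters, 450 or 900 children per facility, and control failure of 2% to 5%. If an odds-ratio bound is compared directly with 1.3 when the true risk ratio is 1.3, it is 3.6%. With the one-sided 95% bound it is 7.6%.

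**Step 6: power cost.**

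- *SAP's risk-difference approximation, 20 facilities of 900 per arm.* SE = √(2 × 0.03 × 0.97 × 2.798 / 18,000) = 0.00301, and 0.009/SE = 2.99. Power is 84.9% with a calibrated z bound and 82.7% with t on 32 df.
- *Log-odds scale, 855 per facility.* Between-facility SD = √(0.002/0.0291) = 0.262. SE = √[(0.262² + 1/(855 × 0.0291)) × 2/20] = 0.104, and ln 1.3/SE = 2.51. Power is about 78% for ML with z, 71% for a calibrated z bound and 68% for t on 32 df. Across calculations the calibrated t analysis gave about 65 to 69%.

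**The case against.** The strongest objection is that the SAP never says maximum likelihood, Wald or z, and it excludes neither t-based nor restricted-likelihood methods. A reader might infer that the planned analysis has a 4.5% error. The documents do not support that: a suitably corrected fit of the same model gives about 2.4%. What stands is that the SAP leaves open a choice that moves the error from about 2.4% to about 4.5%, and that the usual default lies at the wrong end.

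Second, 2.5% is the sample-size alpha, while SAP 6.2 plans a one-sided 95% interval. Read literally, the contrast is 7.5% against 5%, a ratio of about 1.5, so it is too strong to say without qualification that the error nearly doubles. The inflation is present at either level, and the two levels need reconciling anyway.

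Third, the simulations did not fit the patient random effect that SAP 6.2 lists, and the attendance coding is assumed. Hence a range and not a point value.

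Fourth, a reader might extend the figure to antibiotic prescription and the secondary outcomes. They share the model, but error was computed only for clinical failure.

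Finally, the correction might be said to cost the trial its power. On the log-odds settings nominal power falls by about 9 to 12 points relative to ML with z, but most of that is removal of inflated error. A calibrated z bound already gives only 71% there, so the shortfall from 80% comes from the scale and not from the t correction.

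**Conclusion.** The concern holds in conditional form. With 40 facilities, about 8 facility-level parameters and no stated correction, a maximum-likelihood fit with a Wald z bound gives a one-sided non-inferiority error of about 4.5%, range about 4 to 5%, against 2.5%. It is about 3.6% if an odds-ratio bound is set directly against 1.3, and about 7.5% against 5% if the one-sided 95% interval is used.

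This rests on the plan's ICC, failure rate and cluster size, on one attendance term, and on leaving out the patient random effect. Facility-level covariates added by consensus would raise the error; additional facilities, which SAP 3.4 allows, would lower it. The SAP should be changed, because the gating safety claim should not depend on a software default.

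**What to change.** State in SAP 6.2 that the arm comparison uses a small-sample method, and name it. Either of these would serve:

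- a two-stage facility-level analysis adjusted for the stratification factors, with t on 40 minus the number of facility-level parameters (32 under the count above; error about 2.6%); or
- a restricted or pseudo-likelihood fit with Kenward-Roger or Satterthwaite-type degrees of freedom (its error was not simulated here).

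Replacing z by t alone is not enough; the error stays near 4%. Give the attendance categories, and fix any other facility-level covariates in advance, so that the degrees of freedom are known. Reconcile the one-sided 95% interval in SAP 6.2 with the one-sided alpha of 0.025 in SAP 3.3, and state whether the intervals in the figure are one- or two-sided.

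The cost is SAP wording and wider intervals. Power falls about 2 to 3 points relative to a calibrated z bound: 84.9% to 82.7% on the SAP's risk-difference approximation, still above 80%. Measured against the anti-conservative ML/z analysis on the log-odds settings, the nominal fall is about 9 to 12 points, and the sponsor should be told both figures.
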